2.17. Are there any planned subgroup analyses?

For the Term Breech Trial, we found that subgroup analyses were important and helpful for clinicians who were faced with the need to change their clinical practice from vaginal delivery to CS. We therefore plan several subgroup analyses for the Twin Birth Study. For the primary outcome and for the secondary outcome of abnormal neurodevelopment at 2 years, subgroup analyses will be undertaken by parity, gestational age at randomisation, maternal age, presentation of twin B at randomisation, chorionicity and country's national PMR. For the outcome of problematic incontinence, subgroup analyses will be undertaken by parity, maternal age, country's national PMR and history of incontinence prior to pregnancy. Analyses will involve testing for interactions between the factor and treatment group for the outcome.

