2. THE PROPOSED TRIAL

2.1. What is the proposed research design?

To eliminate selection bias, a RCT with prognostic stratification for parity and gestational age at randomisation will be used. Eligible and consenting women will be randomised within parity groups (0 and \geq 1), and within gestational age groups ($32^{0/7}$ - $33^{6/7}$ weeks, $34^{0/7}$ - $36^{6/7}$ weeks, and $37^{0/7}$ - $38^{6/7}$ weeks) to the planned CS group or the planned VB group, using random block sizes. We will not stratify by centre as we anticipate enrolling only a few women in some centres and stratification by centre would predispose to imbalance and pose a threat to allocation masking.

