2.3. What are the planned trial interventions?

2.3.1 Prior to randomisation:

Women with a known or suspected twin pregnancy will be informed about their possible options for delivery. These will include a planned or elective CS, a planned VB with the option to proceed to CS for one or both twins if problems develop during the pregnancy, labour or delivery, or participation in the Twin Birth Study.

2.3.2 Timing of randomisation:

Women with a twin pregnancy at $32^{0/7}$ - $38^{6/7}$ weeks gestation, who meet the selection criteria and consent to participate in the trial, will be randomised. Women may be randomised if they present in labour and/or if they have an indication for urgent delivery (e.g. chorioamnionitis, pre-eclampsia, abruptio placenta) and are otherwise eligible and have given consent.

2.3.3 Timing of Delivery:

Several large studies have shown that the risk of perinatal mortality among twins increases beginning at approximately 38 weeks gestational age, compared with after 41 weeks in the singleton.^{7,8,37-40} For this reason the protocol requests that twin pregnancies be delivered before $39^{0/7}$ weeks gestation either by CS or by inducing labour. Because there is evidence that the risk of neonatal respiratory problems increases if elective CS is undertaken prior to 38 weeks,⁴¹ the ideal time to schedule an elective CS is probably around 38 weeks gestation. If there is uncertainty about the gestational age, consideration may be given to confirming fetal maturity by checking the amniotic fluid L/S ratio or managing the pregnancy expectantly using serial fetal monitoring (twice-weekly non-stress and/or biophysical profile tests) until one is confident that the fetuses are mature. Regardless of the presence of additional risk factors, all women who are undelivered at $38^{6/7}$ weeks gestation should proceed to delivery.

2.3.4 Planned CS Group:

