We wish the sample size to be adequate to find a reduction in risk of perinatal or neonatal mortality or serious neonatal morbidity from 4% to 2% with a policy of planned CS, if such a reduction exists, power = 80%, α error = 0.05 (2- sided). The sample size is thus 1250 pregnancies (or sets of twins) per group or a total N=2500. Since we will be treating each set of twins as a cluster in the analysis of the primary outcome, the power will be somewhat higher than 80% depending on the value of the correlation between members of the same twin pair.⁵⁵ The higher the correlation the less power will be increased. For a correlation of 0.9 the power is increased to 82% and for a correlation of 0.5 the power is increased to 91%. We expect the correlation to be high, and therefore we will require 2500 women and accept the slight increase in power. If we reduced the sample size based on a correlation that is too low, the power would be reduced.

The required sample size does not take into account the reduction in treatment effect caused by women changing their mind about method of delivery, between the time of randomisation and time of delivery. To allow for such crossovers, the required sample has been increased by approximately 10%, to a **total sample of 2800** (1400 women in each group). For the purposes of analysis, patients will be kept in their original randomised groups (intention to treat principle).

Based on our experience with the Term Breech Trial, we will assume a 20% loss to follow-up at 2 years. We estimate the rate of abnormal neurodevelopmental outcome in the planned VB group will be 2% (based on preliminary analysis [from September 2002] of the risk of abnormal neurodevelopmental assessment in the planned VB arm of the Term Breech Trial). A sample size of 2200 clusters of twins will provide >80% power for finding a reduction in risk of abnormal neurodevelopmental outcome from 2% to 0.5%, α error = 0.05 (2-sided).

We estimate the rate of problematic urinary/faecal/flatal incontinence at 2 years following delivery in the planned VB group will be 15% (based on preliminary analysis [from September 2002] of the risk of problematic incontinence in the planned VB arm of the Term Breech Trial). A sample size of 2200 women will provide >90% power for finding a reduction in risk of incontinence from 15% to 10%, α error = 0.05 (2-sided).

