Final analysis: An intention to treat approach, which includes all mothers and fetuses as randomised, will be used. Descriptive statistics (means, standard deviations, proportions) will be calculated to check for any major dissimilarities in the study groups with regard to patient demographics and other baseline information. Methods proposed by Donner and Klar⁵⁷ will be used to compare the rates of the primary outcome, perinatal/neonatal mortality and/or serious neonatal morbidity between the two study groups controlling for the stratification variables (parity $[0, \ge 1]$, gestational age at randomisation $[32^{0/7}-33^{6/7}]$ $34^{0/7}$ - $36^{6/7}$, $37^{0/7}$ - $38^{6/7}$ weeks]) and other prognostic factors (maternal age [<30, \ge 30 years], presentation of twin B at randomisation [cephalic, non-cephalic], chorionicity ⁵⁸ [dichorionic, monochorionic[§]], and the country's national perinatal mortality rate (PMR) (per 1000) as reported by the World Health Organisation ⁵⁹ [<15, 15-20, >20]). Mixed effects models will be used to determine if treatment effects vary between centres and to test for interactions between prognostic factors and treatment. A similar analysis will be performed for the neurodevelopmental outcome. Logistic regression will be used to compare the rates of problematic incontinence at 2 years between groups, controlling for prognostic factors. The level of statistical significance for the analysis of the primary and secondary outcomes will be p < 0.05 (two-sided). Adjusted odds ratios and 95% confidence intervals will be calculated to determine the magnitude of the association between the two study groups and the primary and secondary outcome measures. The number of additional CS needed (number needed to treat) to prevent one adverse outcome will also be calculated.

We will use logistic regression to calculate the adjusted odds ratios and 95% confidence intervals for the comparison of the two study groups with respect to the rates of the following other outcome measures: problematic incontinence at 3 months, satisfaction with the birth experience, depression, and breast feeding. The two study groups will be compared with respect to quality of life (SF-36) using a repeated measures ANOVA. The level of statistical significance for the analysis of the other outcomes will be p < 0.01 (two-sided).

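### Splitting maternal age at 30 years weakens the planned treatment-by-age interaction tests, and the protocol gives no reason for the cut

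*Protocol*

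**What the plan says.** Section 2.16 (final analysis) compares the primary outcome between groups, controlling for the stratification variables and "other prognostic factors (maternal age [<30, \ge 30 years", along with presentation of twin B, chorionicity and national perinatal mortality rate. It then plans mixed effects models "to test for interactions between prognostic factors and treatment". A similar analysis is planned for neurodevelopment, and logistic regression with prognostic factors for incontinence at 2 years.

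Section 2.17 lists maternal age as a subgroup factor for the primary outcome, for neurodevelopment at 2 years and for problematic incontinence. On method it says: "Analyses will involve testing for interactions between the factor and treatment group for the outcome". It does not repeat the cut point, but the two-group definition in 2.16 is the only one the protocol gives.

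Section 2.1 stratifies randomisation by parity and by gestational age, "within gestational age groups ($32^{0/7}$ - $33^{6/7}$ weeks, $34^{0/7}$ - $36^{6/7}$ weeks, and $37^{0/7}$ - $38^{6/7}$ weeks". Maternal age is not a stratum. The protocol gives no reason for cutting at 30, no expected age distribution and no power for any interaction test.

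**The concern.** Cutting a continuous covariate in two treats women of 20 and 29 as alike and women of 29 and 31 as different. If the effect of planned caesarean changes steadily with age, the test on two groups sees only part of that change and is more likely to miss it.

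Section 2.17 explains that subgroup analyses are planned because they helped clinicians who faced a change of practice in the breech trial. A needless loss of power makes a false finding of no interaction more likely in the results meant for that use. Because age is not a stratum, nothing in the design requires the split.

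**Working it through.** **The plan's own figure.** The protocol states no interaction power, so only its main sample size can be reproduced. Section 2.11 plans for "serious neonatal morbidity from 4% to 2% with a policy of planned CS" with "power = 80%, α error = 0.05 (2- sided", and arrives at 1250 per group. The usual two-proportion formula gives [1.96 × √(2 × 0.03 × 0.97) + 0.842 × √(0.04 × 0.96 + 0.02 × 0.98)]² / 0.02² = 1141 per group. With a continuity correction it gives 1239, within 1% of 1250. The planning rates can therefore be used below.

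**Information kept by one cut.** For a normal covariate with a linear effect, cut at c standard deviations (SD) from the mean, the share kept is φ(c)² / [Φ(c)(1 − Φ(c))].

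| Share of women on either side of 30 | Kept | Lost |
|---|---|---|
| 50/50 | 0.637 (= 2/π) | 36.3% |
| 40/60 | 0.622 | 37.8% |
| 30/70 | 0.576 | 42.4% |
| 20/80 | 0.490 | 51% |

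The median cut is the best case for a normal covariate. If age were uniform and cut at its median, 75% would be kept.

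**Effect on an interaction test (two-sided 0.05).** A test with 80% power has an expected z of 1.960 + 0.842 = 2.802. The split multiplies z by the square root of the share kept.
- Normal age, median cut: 2.802 × 0.798 = 2.235, power Φ(0.275) = 61%.
- Normal age, 30/70 cut: 2.802 × 0.759 = 2.126, power Φ(0.166) = 57%.
- Uniform age, median cut: 2.802 × 0.866 = 2.426, power Φ(0.466) = 68%.

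**Illustration on the trial's outcomes.** Assumptions: age SD 5.5 years, mean near 30, and an odds ratio that doubles over 11 years (2 SD), so a slope of ln(2)/2 = 0.347 per SD. The standard error of the interaction per SD is approximately √[1/(n p₀q₀) + 1/(n p₁q₁)].
- *Incontinence at 2 years* (section 2.11: 2200 women, so 1100 per arm, 15% vs 10%; odds ratio 0.45 at age 25 rising to 0.90 at age 36). SE = √[1/(1100 × 0.15 × 0.85) + 1/(1100 × 0.10 × 0.90)] = 0.131, so z = 2.64. Power is Φ(0.68) = 75% with age in years. With the median split, z = 2.64 × 0.798 = 2.11 and power is 56%. A simulation of 2000 trials gave 75.7% and 56.2%.
- *Primary outcome* (1400 per arm, 4% vs 2%, same slope). SE = √[1/(1400 × 0.04 × 0.96) + 1/(1400 × 0.02 × 0.98)] = 0.235, so z = 1.48. Power is 31% with age in years. With the split, z = 1.18 and power is 22%.

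**Other slopes, primary outcome.** Logistic simulation used one binary outcome per pregnancy, N = 2800 and 600 runs per setting. Continuous age versus median split gave 26% vs 18% at 0.3 per SD, 61% vs 44% at 0.5 and 89% vs 73% at 0.7. A 30/70 cut at 0.5 gave 59% vs 33%. With no interaction, both tests rejected in about 4% to 5% of runs.

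**The case against.** **Subgroup results in two age groups are easy to use, and the details could sit in an analysis plan that is not shown.** The first part stands for display: prespecified groups are a sensible way to present results. But section 2.16 states the cut, so this is a choice made in the protocol and not a detail left open. That the cut carries into 2.17 is an inference, though a natural one.

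**The loss depends on assumptions.** This stands. A reader might infer that more than a third of the age information is certainly lost. The protocol supports no such flat figure, because it gives no age distribution and says nothing on the shape of the effect. A uniform distribution cut at the median would lose 25%.

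**Sparse events are the main limit.** This largely stands outside incontinence. The planning rates imply 56 + 28 = 84 primary events and 22 + 5.5, or about 28, abnormal neurodevelopmental outcomes. Age in years does not rescue tests on so few events. The split only makes them weaker.

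**A curvature check uses up some of the gain.** If linear and squared interaction terms are tested jointly on 2 df, a truly linear trend detectable with 80% power on 1 df is detected with 71%. That is still above 61%, but by less.

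**Coarse adjustment.** A reader might infer that adjusting for two age groups biases the treatment comparison. It does not: allocation is randomised, and the cost is at most some precision.

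**Gestational age.** A reader might extend the criticism to the three gestational-age bands. The protocol does not support that. The bands are the randomisation strata, so adjusting for them in that form is proper. Section 2.3.3 says "the risk of neonatal respiratory problems increases if elective CS is undertaken prior to 38 weeks", but also that perinatal mortality rises from about 38 weeks. Those are opposite changes around one point, and they concern gestation at delivery, whereas the analysis uses gestation at randomisation. Which test is stronger depends on the shape. With gestation assumed uniform over the 49 eligible days and a linear trend, 80% power falls to 65% with a 2-df band test. If instead the effect differs only from 37 weeks on, a band test with 80% power compares with 68% for a linear term.

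**Conclusion.** The concern holds for maternal age only. The protocol fixes a two-group split for a covariate that is not a stratum, gives no reason for it, and on the natural reading uses it for the interaction tests.

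Under approximate normality and a linear trend on the logit scale, at least 36% of the information is lost and 80% power becomes about 61% or less. The practical gain from correcting it is clearest for incontinence (75% against 56% in the illustration). For the primary outcome it is small in absolute terms (31% against 22%), because power is low either way. The treatment comparison remains valid. This is a worthwhile improvement and not a flaw that threatens the trial's conclusions.

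**What to change.** In sections 2.16 and 2.17, enter maternal age in years as a continuous term, both for adjustment and for the treatment interaction. Name the 1-df linear interaction as the test, with a squared term as a check for curvature. Keep the under-30 and 30-or-older groups only to display subgroup results.

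Leave the gestational-age bands as they are. A continuous gestational-age interaction is optional and not clearly better.

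The cost is a change of wording. It assumes that age or date of birth is recorded. The protocol does not say so outright, but the means and standard deviations it plans for demographics suggest it. The downside is some reliance on an approximately linear trend, which the curvature check addresses in part.

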2.18. Has any pilot study been carried out using this design?

The Term Breech Trial serves as a pilot for the proposed Twin Birth Study: this study uses similar methods of recruitment, randomisation and data collection, and the outcomes are measured in similar ways. In addition, a pilot study⁵⁵ was undertaken to ascertain the willingness of women to join a study such as the Twin Birth Study. Women presenting with twin pregnancies (at 28-37 weeks gestation) at Sunnybrook and Women's College Health Science Centre and Mount Sinai Hospital, Toronto, were asked, after they had read the patient information sheet and consent form, if they would be willing to take

[§] centres should determine or confirm chorionicity by placental pathology for all same sex twins

part in the Twin Birth Study. Results indicate that 48% of those approached would be willing to take part. We have used this information in estimating the likely recruitment rate and number of centres needed for the trial (sections 2.12 and 2.15).

3. TRIAL MANAGEMENT

3.1. What are the arrangements for day-to-day management of the trial?

The trial will be managed on a day to day basis, in MIRU, by a small working group which will include [name], [name] (the MIRU Director), [name] (MIRU Research Manager) and the Study Staff (Trial Co-ordinator, Data Manager, Research Assistant). This group will meet weekly.

3.2. What will be the role of each applicant?

[name] is the Principal Investigator and is responsible for the progress and timely completion of the trial. [name], [name], [name], [name] and [name] are responsible for responding to clinical queries, visiting sites, and for encouraging recruitment, protocol compliance and accurate and complete data collection. [name] (the MIRU Director) is responsible for the work of the Data Co-ordinating Centre, including the distribution of funds, the administration of the study, and for providing advice based on previous experiences with the co-ordination of multicentre RCTs. [name] is responsible for providing advice on the neonatal outcomes. [name] is responsible for providing advice on the neurodevelopmental assessments. [name] is responsible for providing advice on methodological issues and for assisting with posthoc secondary analyses of the dataset. [name], [name] and [name] (the MIRU Director) are responsible for the statistical analyses. All applicants are responsible for assisting with recruitment efforts, including participation in collaborators' meetings, being advocates for the study locally, nationally, and internationally, visiting collaborating centres and attending scientific meetings to present the study results when appropriate.

3.3. Describe the trial Steering Committee and the DSMB

The Steering Committee is responsible for the conduct of the study. The Steering Committee, which includes all applicants, the MIRU Research Manager ([name]) and the Trial Staff, meets every 2-3 months. A consumer ([name]) has also joined the Steering Committee. Four members of the Steering Committee ([name], [name], [name], [name]) will form an adjudication subcommittee to review the primary outcomes, masked to allocation group and method of delivery, to confirm that they have or have not occurred. The DSMB, which includes [name], Professor, Department of Epidemiology and Public Health, Yale University School of Medicine (chair); [name], Resource Centre for Randomised Trials, Nuffield Department of Clinical Medicine, University of Oxford; [name], Professor, Department of Pediatrics, University of Texas Health Science Center at Dallas; [name], Chair, Department of Epidemiology and Biostatistics, The University of Western Ontario; [name], Department of Obstetrics and Gynaecology, Coombe Women's Hospital; will be responsible for the review of the interim analysis and for recommending early termination of the study, if necessary, to the Steering Committee. The trial will be conducted according to the Good Clinical Practice guidelines.⁶⁰

